6. **Parent Rated Autism Symptomatic Change Scale (PRASC):** The PRASC is a 12-item questionnaire that asks parent to rate changes in symptoms from “much better” to “much worse” on a 7 point Likert scale from the beginning of the intervention. This instrument was developed by [name] and Rossignol (2010) and produces a reliable measure of changes. The parent will be asked to complete this scale at each remote and onsite visit following randomization to monitor changes in ASD symptoms in the study.

Table 1. Schedule of Measures		Screening	Baseline	Double blind Phase							
Measure	Pre-Screening			*1 wk	*2 wk	*4 wk	*8 wk	12 wk	*16 wk	*20 wk	24 wk
Phase 1											
Phase 2											
Parent Ratings											
Demographics		X									
Vineland III Caregiver Form [1]			X					X			X
ABC [2]		X						X			X
PRAS-ASD [3]			X					X			X
CGSQ-Short form [4]			X					X			X
Sensory Profile 2 [5]			X								
PRASC [6]						X	X	X	X	X	X
Laboratory Assessments											
Safety Laboratory [7]	X							X			X
Biomarker Laboratories [8]	X							X			X
Pregnancy (B-HCG)	X										X
Vital Signs	X										
Height and Weight	X		X					X			X
Head Circumference	X										
Medical Assessments											
Medical/Psych History [9]		X									
Physical Exam		X									
Adverse Effects Review			X	X	X	X	X	X	X	X	X
Concomitant Treatments	X	X	X	X	X	X	X	X	X	X	X
Suicidality Assessment [10]		X	X			X	X	X	X	X	X
Compliance				X	X	X	X	X	X	X	X
Developmental Assessments											
CARS [11]		X						X			X
DAS [12]		X						X			X
OACIS [13]			X					X			X
CGI-Severity [14]			X					X			X
CGI-S-ASD			X					X			X
CGI-Improvement [15]								X			X
CGI-I ASD								X			X
Parent Target Problems [16]			X					X			X
CYBOCS-ASD [17]			X					X			X
Other Assessments											
Eye tracking task [18]			X					X			X

Full Study Title: Effect of a Wide Spectrum Nutritional Supplement on Mitochondrial Function in Children with Autism Spectrum Disorder (ASD)

Principal Investigator: [name]; Co-Investigators: [name]

Sponsor: [name]; IND 142751; ClinicalTrials.gov ID: NCT03835117; Protocol Version 02/11/2022

Funding Source: Turnabout for Autism (Private Foundation), Pleasanton CA.

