## 5. RESEARCH PLAN

### Trial Design

50 children with ASD and signs and symptoms of abnormal mitochondrial activity will be randomized in 1:1 ratio to receive a wide-spectrum nutritional supplement that targets mitochondrial function or placebo for 12 weeks under DBPC conditions. Each participant will serve as their own control in the cross-over design. Using a phone screen, we will identify children (age  $\geq$  2:6 and  $<$  17:3) with a diagnosis of ASD and evidence of mitochondrial function which is significantly higher or lower than average (here forth referred to as mitochondrial dysfunction). Children with suspicion of mitochondrial dysfunction will be invited to participate in a screening visit to make sure they meet including and exclusion criteria. If the screening visit is longer than 6 weeks from the prescreening, we will repeat the baseline metabolic testing to ensure an accurate baseline mitochondrial measurement. If they meet criteria, the baseline visit will be completed within 2 week but we will attempt to complete it on the same day (Table 1). Upon successful completion of the baseline visit, the participant will enter Phase 1 of the trial and will be randomized to receive active treatment or placebo for 12 weeks under DBPC conditions. At the end of the 12 weeks (end of Phase 1), the participant will return for evaluations similar to the ones conducted at baseline. Upon successful completion of the post-Phase 1 visit, the participant will start Phase 2 where they will receive active treatment or placebo, depending on what they received during Phase 1 – they will be crossed over to the opposite treatment regimen. Potential AEs, compliance and concomitant treatments will be monitored every four weeks.

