## **Laboratory Assessments**

7. **Safety laboratories**: Safety labs will be measured at the screening visit. These will include a complete blood count and a comprehensive metabolic panel.
8. **Biomarker**: Most biomarkers will be collected at baseline and after each treatment arm to determine if the treatment results in a change in these biomarkers. Baseline biomarkers will help understand whether treatment response can be predicted from biomarker tests.
  - a. Buccal swabs will be collected to assess mitochondrial function.
  - b. Plasma, Peripheral Blood Mononuclear Cells (PBMCs), DNA, and RNA will be collected and stored locally for future analysis, such as oxidative and methylation metabolism, bioenergetics, immune biomarkers, gene expression, epigenetics, and gene sequencing. 3billion Laboratory in Seoul, South Korea will perform genetic sequencing to look for causative mutations if good quality DNA is obtained and can be isolated. Samples will be stored until they are used up or destroyed, when possible. The PI, [name], will retain control over the blood sample unless it is requested that the sample be destroyed and then it will not be used for any future studies. If the participant wishes to have the sample removed from storage and destroyed at any time, they may contact a study coordinator or PI. IRB permission will be obtained prior to sharing samples for future studies. These samples will be de-identified and no protected health information will be shared with collaborators. If samples are shared, a log of those who withdraw samples will be documented thoroughly.
  - c. Deciduous teeth and hair samples will also be collected and sent to [name] laboratory. Recent research suggests prenatal nutritional metal concentrations measured in deciduous teeth correlate with long-term language development and may predict treatment response and other recent studies support the measurement of unique metabolic markers using hair samples.
  - d. Folate receptor  $\alpha$  autoantibody (FRAA) titers will be sent to the laboratory of [name], Ph.D. at the State University of New York, Downstate (Brooklyn, NY) or Iliad Neurosciences. We have demonstrated in one study that FRAA are related to methyl-B12 metabolism.

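### The pregnancy test is not repeated at week 12, so placebo-first girls to whom it applies start active product on a result at least 12 weeks old

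*Combined protocol and SAP*

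**What the plan says.** Table 1 (Schedule of Measures, section 5 of the combined protocol and SAP) has eleven visit columns, from Pre-Screening to week 24. The row "Pregnancy (B-HCG") carries a mark at Pre-Screening and at week 24, and nowhere else. The rows "Safety Laboratory [7"] and "Biomarker Laboratories [8"], directly above it, carry marks at Pre-Screening, week 12 and week 24. Item 7 under Laboratory Assessments says of the safety laboratories: "These will include a complete blood count and a comprehensive metabolic panel". Blood is therefore already due at week 12.

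Trial Design sets out the crossover. Each child takes active product or placebo for 12 weeks and attends the end-of-Phase-1 visit. On completing that visit, "the participant will start Phase 2 where they will receive active treatment or placebo", whichever was not given in Phase 1. No washout is described and no pregnancy result is required at that point.

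Girls are eligible up to just under 17 years 3 months. The exclusion criteria do not name pregnancy, although a general criterion on medical conditions and laboratory findings could be used to exclude.

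**The concern.** By scheduling a pregnancy test before treatment, the plan chose to check for pregnancy ahead of exposure to the product. In a parallel-group trial one pre-treatment test would do this for everyone. In a crossover it does so only for the sequence that receives active product first. For the other sequence, first active exposure comes at week 12, and the schedule has no test between Pre-Screening and the end of the study.

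What is at stake is a conception during the placebo phase. It could go unnoticed, and the girl would then begin up to 12 weeks of active dosing. The next scheduled test, at week 24, would come after that dosing was complete. The plan's own precaution is thus applied unevenly between the two sequences, although a visit with laboratory work already exists at the point where it is needed.

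**Working it through.** The plan states no figure on this point, so there is nothing to reproduce. The check has three steps.

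**1. Is the blank at week 12 real?** Table 1 was read from a PDF, so a shifted cell has to be ruled out. Setting rows against the eleven visit columns gives:

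| Row | Cells | Marked at |
|---|---|---|
| Safety Laboratory | 11 | Pre-Screening, 12, 24 |
| Biomarker Laboratories | 11 | Pre-Screening, 12, 24 |
| Pregnancy | 11 | Pre-Screening, 24 |
| Height and Weight | 11 | Pre-Screening, Baseline, 12, 24 |
| Concomitant Treatments | 11 | all eleven columns |

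The pregnancy row has the same number of cells as the others, and its two marks fall in the right columns. The blank at week 12 is not an extraction shift.

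**2. Does other text supply the missing test?**
- Trial Design says the end-of-Phase-1 evaluations resemble those at baseline. The pregnancy test is not marked at Baseline either, so this adds nothing.
- Trial Design also has a repeat rule: "If the screening visit is longer than 6 weeks from the prescreening, we will repeat the baseline metabolic testing". It does not name the pregnancy test. Even if it were taken to include it, the repeat would come before randomisation.
- Adverse-event reviews are interviews, not tests.

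No visible text schedules a test between the start of treatment and week 24.

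**3. How old is the result at first active dose?** Let *g* be the time in weeks from the pre-treatment sample to the first dose of Phase 1, with *g* ≥ 0. Phase 1 lasts 12 weeks and Phase 2 another 12 (Trial Design).

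- Active-first: age at first active dose = *g*.
- Placebo-first: age at first active dose = *g* + 12 ≥ 12 weeks.
- Interval between the two scheduled tests = *g* + 24 ≥ 24 weeks.

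Only the lower bounds are firm. The documents limit one part of *g* ("the baseline visit will be completed within 2 week" of screening), but give no maximum for Pre-Screening to screening, no interval from baseline to first dose, and no visit windows.

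With a week-12 test taken before Phase 2 dispensing:

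- Placebo-first: age at first active dose falls from at least 12 weeks to about 0.
- Intervals between tests become *g* + 12 and 12 weeks, in place of *g* + 24.
- Active dosing between tests can still last up to 12 weeks: weeks 0 to 12 for active-first, weeks 12 to 24 for placebo-first.

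So the added test prevents exposure from a detectable placebo-phase conception. For active-first girls it brings detection forward but prevents no active exposure, because their active dosing ends at week 12.

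**The case against.** The strongest reply is that no harm is shown. The documents name no fetal hazard. Their one remark on dosing in pregnancy, under Investigational Product, is reassuring: the folate dose is put at about half of one commonly recommended to certain women who may become pregnant. Potential Risks describes a widely used supplement with few reported side effects. This stands, and it is why the point is minor. The folate remark covers only part of a 34-ingredient product, however, and the plan itself judged a pregnancy test worth doing.

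A second reply is that a week-12 test leaves the larger window open, since a girl who conceives after starting active product is exposed for up to 12 weeks with or without the change. That is correct. The change addresses only the start of active dosing in the placebo-first sequence.

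Third, few girls may be concerned. Eligibility begins at 2 years 6 months, and Table 1 does not say who is tested. Under 1:1 allocation about half of the applicable girls would be placebo-first on average, but the total is unknown, so no probability of an affected girl can be drawn from the documents.

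Fourth, contacts at least every four weeks include an open question about problems and one about health-care encounters, which could bring a known pregnancy to light. They would not find an unrecognised one. Consent pages were removed, so pregnancy instructions there cannot be ruled out. They would not change the test schedule in Table 1.

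A reader might also infer that the pre-treatment pregnancy test belongs at the screening visit, because item 7 states "Safety labs will be measured at the screening visit". The documents do not support that. Item 7 lists the blood count and metabolic panel and does not mention B-HCG, which only Table 1 places. Where the first sample is drawn does not affect the 12-week lower bound.

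**Conclusion.** The point holds as a minor safety improvement. Following Table 1 exactly, placebo-first girls to whom the test applies start active product on a pregnancy result at least 12 weeks old, and the only later test comes after all dosing. The bound rests on the sample being taken before randomisation and on Phase 1 lasting its stated 12 weeks.

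A reader might go further and conclude that the product endangers a fetus, that a substantial number of girls would be exposed, or that the trial's results are compromised. None of these follows. No hazard is named, no count of tested girls is given, and the primary analysis of mitochondrial function does not depend on when pregnancy is tested.

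**What to change.** Add B-HCG to the 12 wk column of Table 1 for applicable girls, as a urine test or from the week-12 blood draw already scheduled. State in Trial Design that a negative result is required before Phase 2 product is dispensed.

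The cost is one inexpensive test per applicable girl at an existing visit, plus the amendment wording. If blood is used, Phase 2 dispensing waits briefly for the result; a urine test at the visit avoids this.

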### Procedures

Randomization: Randomization will be carried out within site using permuted blocks of 4 subjects without additional stratification to nutritional supplement or placebo in a 1:1 ratio. Statisticians will prepare the permuted blocks for each site and will be sent to the Investigational Pharmacist at each site. Investigators and study staff will be blind to the allocation sequence.

**Compensation** Participants will be compensated \$50 for each of the four physical visits.

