## **Potential Risks**

The risks associated with these procedures include exposure to the study supplement or placebo, and the risk associated with venipuncture. The blood draws poses a possible risk of bruising at the site of the draw, light-headedness and fainting along with a remote chance of infection.

Although highly unlikely, there are potential privacy risks associated with participating in such a study. There is minimal risk associated with the completion of rating scales and assessment measures. Blood draws are common procedures and will be performed by a certified phlebotomist. We will offer a numbing cream prior to the blood drawing procedure. We will systematically review adverse at follow up phone calls and clinic visits (see below). Parents will be given phone numbers of the principal investigator and study physician – who will be available after hours. The PI and study physician have access to the pharmacy after hours – if it is necessary to break the blind.

The nutritional supplement and supplements similar to it have been on the market and used widely in the autism community. There have been few reported side effects of this supplement. They include nausea and hyperactivity, both of which resolve on their own. One similar supplement produced by [name] at Arizona State University has been studied in three clinical trials without reported significant adverse effects. In addition, the majority of the ingredients in the nutritional supplement are well within the proposed upper tolerable limits recommended by the institute of medicine and the two vitamins that exceed these limits are known to be well tolerated at doses well above the recommend upper limits. Increased consumption of B vitamins may also temporarily change urine color.

Confidentiality will be maintained throughout the project period. With the exception of tests that require date of birth, research records will not include names or contact information. Subjects will be identified only by their code numbers. A file with personal health information (e.g., names and addresses) will be kept separately in a locked file cabinet.

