### **Monitoring for Adverse Events (AEs):**

At each visit, including baseline and interim contacts, the treating clinician will systematically review for AEs and concomitant medications using an AE Review form developed for this study. We have used versions of this form, in several multi-site clinical trials in children with ASD which contains a general inquiry including several questions about daily activities (e.g., sleep, appetite, energy level, bowel and bladder functions). The general inquiry includes an open-ended question about any problems or complaints, as well as questions regarding the need for other medications and doctor or health care encounters since the last study visit. The last section includes specific questions about daily activities. All **new** AEs will be documented on the AE log. The status of previously-reported AEs

Full Study Title: Effect of a Wide Spectrum Nutritional Supplement on Mitochondrial Function in Children with Autism Spectrum Disorder (ASD)

Principal Investigator: [name]; Co-Investigators: [name]

Sponsor: [name]; IND 142751; ClinicalTrials.gov ID: NCT03835117; Protocol Version 02/11/2022

Funding Source: Turnabout for Autism (Private Foundation), Pleasanton CA.

will be monitored as well.

When the treating clinician elicits an AE, it will be documented regardless of suspected relationship to the supplement. The AE log requires the treating clinician to label the AE and to document the severity, onset, course, outcome, and attribution (study drug related or not).

Attribution is classified as follows:

- Definite: AE is clearly related to the study drug.
- Probable: AE is likely to be related to the study drug.
- Possible: AE may be related to the study drug.
- Unlikely: AE is doubtfully related to the study drug.
- Unrelated: AE is clearly not related to the study drug.

*Severity of AEs is classified as follows:*

- mild = present, but no intervention required;
- moderate = present, may be bothersome or may require intervention;
- severe = present, bothersome, requires intervention and may produce sequelae.

Decisions on the appropriate care of the subject will be made by the treating clinician (who will remain blind to treatment assignment), in collaboration with the family's primary care provider whenever possible. Abnormal findings on laboratory tests that exceed established alarm values will be investigated to determine the nature of the adverse events.

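### Early adverse-event and compliance contacts follow the first treatment start but not the second, so placebo-first children have no scheduled review for four weeks after their first active dose

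*Combined protocol and SAP*

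**What the plan says.** The schedule of measures (Table 1, section 5) has post-randomisation columns at weeks 1, 2, 4, 8, 12, 16, 20 and 24. The row "Adverse Effects Review" is marked in all of them and at baseline. The compliance and concomitant-treatment rows are also marked in all eight. No column lies between week 12 and week 16.

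The Trial Design section describes the same monitoring differently: "Potential AEs, compliance and concomitant treatments will be monitored every four weeks".

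On the design, "50 children with ASD and signs and symptoms of abnormal mitochondrial activity will be randomized in 1:1 ratio", and at the end of week 12 "they will be crossed over to the opposite treatment regimen". The Procedures section confirms allocation "without additional stratification to nutritional supplement or placebo in a 1:1 ratio".

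On elicitation, the adverse-event monitoring section says: "At each visit, including baseline and interim contacts, the treating clinician will systematically review for AEs and concomitant medications". The form has an open question about problems, and asks about other medications and "doctor or health care encounters since the last study visit". The Potential Risks section says of the few side effects reported so far: "They include nausea and hyperactivity, both of which resolve on their own". It also gives parents telephone numbers for the principal investigator and the study physician.

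**The concern.** A crossover has two treatment starts. Table 1 counts its early contacts from randomisation, so they cover only the first. For a child on placebo first, the week-12 visit closes Phase 1 before any active dose is taken, and the next scheduled contact is week 16.

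The side effects named in the protocol are of a self-limiting kind. A mild one, which by the plan's own grading needs no intervention, would probably not lead to a new medication or a health care visit. At week 16 it would then depend on the open question and on a parent's memory of the preceding four weeks. Compliance has the same gap: a child who refuses the product after the switch could go 4 of 12 treatment weeks without a scheduled check.

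At stake are early safety observation in about half the children, the adverse-event frequencies and exploratory time-to-event analyses in the Statistical Analysis section, and the adherence data behind the per-protocol analysis. The primary mitochondrial outcome is not affected. The plan states no figure on this point that could be reproduced.

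**Working it through.** **Inputs.** Contact weeks come from Table 1. Crossover at week 12, 50 children and 1:1 allocation come from Trial Design and Procedures, giving 50 / 2 = 25 children per sequence.

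**Contacts by time since treatment start.**

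- Phase 1: weeks 1, 2, 4, 8, 12. Five contacts, with gaps of 1, 1, 2, 4 and 4 weeks.
- Phase 2: 16 − 12 = 4, 20 − 12 = 8, 24 − 12 = 12. Three contacts, with gaps of 4, 4 and 4 weeks.

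**Scheduled reviews by sequence and treatment, all children completing.**

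| Sequence | On supplement | On placebo |
|---|---|---|
| Supplement first | 25 × 5 = 125 | 25 × 3 = 75 |
| Placebo first | 25 × 3 = 75 | 25 × 5 = 125 |
| Total | 200 | 200 |

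The imbalance lies between periods and sequences. The treatment totals are equal.

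**If Trial Design governs instead.** Both phases have contacts at 4, 8 and 12 weeks, and each treatment has 2 × 25 × 3 = 150 reviews. The asymmetry disappears, but no child then has a contact before week 4 of either phase.

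**Delay to review (assumption: onset uniform over the first 14 days after a start).**

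- Phase 1: the next review is on day 7 or day 14, so the mean wait is 7 / 2 = 3.5 days.
- Phase 2: the next review is on day 28, so the mean wait is 28 − 7 = 21 days, ranging from 14 to 28.

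Share of events still present at that review, for assumed durations:

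- 3 days: 3 / 7 = 43% in Phase 1, 0% in Phase 2.
- 7 days: 100% and 0%.
- 14 days: 100% and essentially 0%.

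**Effect on observed rates (all values assumed).** Let early events be detected with probability 0.90 in Phase 1 and s in Phase 2, whichever treatment is taken. Pooled detection on each treatment is (0.90 + s) / 2, which is 0.70 at s = 0.50 and 0.90 at s = 0.90. True early rates of 20% on supplement and 10% on placebo would then read:

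- s = 0.50: 14% and 7%, a ratio of 2.0 and a difference of 7 points.
- s = 0.90: 18% and 9%, a ratio of 2.0 and a difference of 9 points.

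The absolute rates and their difference shrink, while the ratio does not move. Within the supplement, the two sequences would read 18% and 10% at s = 0.50 for the same true rate.

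**Dropout.** If a supplement-first and b placebo-first children leave at the end of Phase 1, reviews on supplement are 125 + 3(25 − b) and on placebo 125 + 3(25 − a). The difference is 3(a − b). Unequal loss between sequences breaks the balance; equal loss does not.

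**The case against.** Four points can be made for the plan.

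- Parents can telephone at any time, so the children are not out of contact. This stands: what is missing is scheduled contact.
- A resolved event can still be recorded at week 16. The open question can bring it out, the log takes onset, course and outcome, and the analysis counts each event once at its highest severity. This also stands, so it would go too far to infer that such events are missed. The open question has no stated recall window, however, and the question on encounters since the last visit would not catch a mild event that led to none.
- The crossover balances period across treatments. This stands for the pooled comparison. A reader might infer from the 125 against 75 reviews that the supplement's event rate is understated relative to placebo. The documents do not support that, because supplement-first children take placebo under the same sparse Phase 2 schedule. The plan sets out no comparison between sequences.
- The protocol gives no onset time or duration for the side effects and no reason for the week-1 and week-2 contacts. It cannot be said that the plan judged those contacts necessary, and the delay and detection figures above are illustrations only.

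The difference between Trial Design and Table 1 might be dismissed as a summary of the interval. Even so, the two give different contact schedules for Phase 1, and site staff could follow either.

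**Conclusion.** The point holds in a limited form. Under Table 1, about 25 of 50 children have no scheduled safety or compliance contact for four weeks after their first active dose, and their on-supplement reviews number 75 against 125 in the other sequence. Early self-resolving events in Phase 2 are likely to be under-reported, or captured only by recall or a parent-initiated call. The result is lower sensitivity and ascertainment that differs by period and sequence. It is not a bias toward one treatment in the pooled comparison, provided all children complete or losses before Phase 2 are equal between sequences.

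The contact counts rest on Table 1 and on 25 children per sequence. The size of any under-reporting cannot be derived from the documents. This is an inexpensive improvement to safety and adherence data and does not threaten the primary analysis.

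**What to change.** 1. Reconcile Trial Design with Table 1 so that both give the same contact weeks in each phase.
2. Collect adverse-event, concomitant-treatment and compliance data on the same schedule after both treatment starts, for all children whatever their sequence, so that the blind is kept. Repeating Table 1's own week-1 and week-2 remote contacts after the crossover, at weeks 13 and 14, would achieve this. Scheduled reviews on the supplement become 125 in each sequence, each treatment has 250 in total, and the longest gap from the first active dose to the next scheduled contact falls from four weeks to one.

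The cost is 2 × 50 = 100 short calls at most, with the existing form and staff, a small amendment and slightly more burden on families.

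Restricting the adverse-event comparison to contacts common to both phases should not be used as a substitute. Only new events are logged at each contact. An event first recorded at week 1 or 2 of Phase 1 would therefore be dropped, while the same event elicited at week 16 would be kept. That discards recorded safety data and reverses the asymmetry.
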